**Part 2: MAD**

Cohort	N	Dose	Drug administration
7	6:2	10 mg/kg	ARGX-113 or placebo every 4 days on 6 occasions
8	6:2	25 mg/kg	ARGX-113 or placebo every 7 days on 4 occasions
9	6:2	Either 10 mg/kg 	ARGX-113 or placebo every 7 days on 4 occasions
		Or 25 mg/kg 	ARGX-113 or placebo every 4 days on 6 occasions
10	6:2	25 mg/kg	ARGX-113 or placebo every 7 days on 4 occasions

An interval of at least 14 days between dosing of the first subject of each MAD dose level will be observed.

active:placebo

Doses are based on weight at Day -1. Starting dose and dosing interval to be confirmed following SAD study. The doses administered for the Part 2 MAD study were determined following review of the blinded safety, PK and PD data (as available) from the Part 1 SAD study and are based on the lowest observed IgG measurement (IgG nadir) and time to IgG nadir (IgG tnadir).

Dose and dosing schedule will be chosen based on blinded results obtained from Cohorts 7 and 8. After dosing was stopped in Cohort 8, it was decided to dose 10 mg/kg every 7 days in Cohort 9. Per amendment 4, an additional Cohort 10 was added.

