#### Pharmacodynamics

Pharmacodynamic assessments will be conducted for the SAD and MAD studies to measure for the total immunoglobulin G (IgG), IgG subtype (IgG 1, IgG 2, IgG 3, and IgG 4), IgA, IgD, IgE and IgM levels.

The PD effect will be measured by endogenous immunoglobulin concentration versus baseline change (in %). The following parameters will be calculated, where appropriate, from individual data of total IgG, IgG subtypes (1, 2, 3, and 4), IgA, IgD, IgE, IgM change from baseline:  $E_{\max}$ ,  $t_{E_{\max}}$ , and AUEC.

Unlike total IgG and IgG subtype levels, no changes in IgA, IgD, IgE, IgM levels are to be expected based on FcRn biology and pre-clinical data. As such, the abovementioned parameters will only be calculated for these types of immunoglobulins if a PD effect is observed.

The relationship between ARGX-113 concentration and total IgG or IgG subtypes 1, 2, 3, and 4, change from baseline values will be graphically presented. If appropriate, graphical relationship between main PK and PD parameters will also be assessed.

The PK/PD relationship will be assessed graphically.

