##### Pharmacokinetics

- In the SAD part, proportionality between the dose administered and the PK parameters will be assessed by means of a mixed-effects analysis of variance (ANOVA) model with cohort and dose (nested within cohort) as fixed effects, and subject (nested within cohort) as random effect in the model on the following ln-transformed ARGX-113 parameters:  $C_{\max}/\text{dose}$ ,  $C_{72\text{h}}/\text{dose}$ ,  $\text{AUC}_{0-72\text{h}}/\text{dose}$ ,  $\text{AUC}_{\text{inf}}/\text{dose}$ , total Ae %,  $\text{CL}_{\text{R}}$  and  $t_{1/2,\lambda_z}$  (if possible). In case of significant dose effect observed on these parameters, comparison between doses will be performed using Tukey's test. As  $t_{\max}$  is a discrete variable dependent on selected blood sampling times, dose effect will be assessed using a non-parametric Kruskal-Wallis test and in case statistically significant, applying Wilcoxon's rank sum test with Moses' 90% confidence intervals for pairwise comparisons.
- In the MAD part, proportionality between the dose administered and the PK parameters will be assessed, when appropriate, by means of a mixed effects model on ln-transformed ARGX-113 ( $C_{\max}/\text{dose}$ ,  $C_{72\text{h}}/\text{dose}$  or  $C_{168\text{h}}/\text{dose}$ ,  $\text{AUC}_{72\text{h}}/\text{dose}$  or  $\text{AUC}_{168\text{h}}/\text{dose}$ , and  $t_{1/2,\lambda_z}$ ) with random subject effect and with day, dose and dose\*day interaction as fixed effects. The dose effect on ln-transformed  $R_{\text{ac}}$  will be evaluated from a mixed effect analysis of variance with dose as fixed effect and subject as random effect. As  $t_{\max}$  is a discrete variable dependent on selected blood sampling times, the dose effect will be assessed using a non-parametric Wilcoxon's rank sum test plus 90% CIs. The day effect will be tested using the non-parametric Wilcoxon's signed ranks test.

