##### Pharmacodynamics

- In the SAD part, percent change at each postdose time point for IgG, AUECs and  $E_{\max}$  will be compared between the treatment groups (placebo subjects pooled) using an ANOVA model with treatment as fixed effect. In case of a significant treatment effect, pairwise comparison between treatments will be performed using Tukey's test.  
As  $t_{E_{\max}}$  is a discrete variable dependent on selected blood sampling times, comparison between treatment groups (placebo subjects pooled) will be assessed using a non-parametric Kruskal-Wallis test and in case statistically significant, applying Wilcoxon's rank sum test with Moses' 90% CIs for pairwise comparisons.

- 
- In the MAD part, percent change at each postdose time point for IgG, AUECs and  $E_{\max}$  will be compared, when appropriate, between the treatment groups (placebo subjects pooled), separately for each administration day, using an ANOVA model with treatment as fixed effect. In case of a significant treatment effect, pairwise comparison between treatments will be performed using Tukey's test.

As  $t_{E_{\max}}$  is a discrete variable dependent on selected blood sampling times, comparison between treatment groups (placebo subjects pooled) will be assessed using a non-parametric Kruskal-Wallis test, with pairwise comparisons using Wilcoxon's rank sum test plus 90% CIs (only in case the overall dose effect is statistically significant). The day effect will be tested using the non-parametric Wilcoxon's signed ranks test.

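### Ranking pooled placebo in the Kruskal-Wallis test of time to maximum IgG effect costs much of its power to detect a dose difference, and can produce a rejection that the MAD text would label a dose effect

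*Protocol*

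**What the plan says.** The analysis is fixed in the Protocol Synopsis, Statistical Methods, Pharmacodynamics. It treats tEmax as a variable that "is a discrete variable dependent on selected blood sampling times" and states for both SAD and MAD that "comparison between treatment groups (placebo subjects pooled) will be assessed using a non-parametric Kruskal-Wallis test".

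The test is a gate. In SAD the plan continues: "in case statistically significant, applying Wilcoxon's rank sum test with Moses' 90% CIs for pairwise comparisons". In MAD the pairwise Wilcoxon tests are run "only in case the overall dose effect is statistically significant", so the MAD text reads the overall result as a statement about dose.

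Two neighbouring rules differ:
- Criteria for Evaluation, Pharmacodynamics: no change is expected in IgA, IgD, IgE and IgM, and "the abovementioned parameters will only be calculated for these types of immunoglobulins if a PD effect is observed". No such condition covers IgG in placebo subjects.
- Statistical Methods, Pharmacokinetics (SAD): for tmax, "dose effect will be assessed using a non-parametric Kruskal-Wallis test". Only active doses can enter that test.

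**The concern.** A time of maximum effect has meaning only where there is an effect. For percent change, AUEC and Emax, placebo supplies a useful reference value near zero. For tEmax it supplies none: the value is wherever on the sampling grid the random minimum happened to fall. Ranking those times with the active times mixes two questions: whether time to nadir differs between doses, and whether placebo scatter is centred somewhere other than the active nadirs.

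Two consequences follow. Placebo values at both ends of the ranking push the dose groups together in the middle, so a real dose difference is harder to see, and a missed gate blocks every dose-to-dose comparison of tEmax. Conversely, if active nadirs lie away from the centre of the placebo scatter, the test can reject although all doses behave alike.

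**Working it through.** **Figure to reproduce.** None. The protocol gives no alpha, power or effect size for this test and states that no formal sample size calculation was made.

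**Inputs from the protocol**
- SAD, per cohort: 1:1 sentinels then 3:1, so 1 + 3 = 4 active and 1 + 1 = 2 placebo. Five cohorts give 5 x 4 = 20 active and 5 x 2 = 10 placebo. Six give 24 and 12.
- MAD, per cohort: 6:2. Four cohorts give 4 x 6 = 24 active and 4 x 2 = 8 placebo.
- SAD post-dose PD samples (Time and Events Schedule, Part 1): 2, 4, 8, 24, 48, 72, 96, 144, 336, 504, 672 h. That is 11 times, 7 of them at or before 96 h.

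**Assumptions**
- Alpha is 0.05.
- Active tEmax has 50% of its mass at a centre time and 25% at each neighbouring sample.
- Placebo tEmax is the time of the minimum of noise, either uniform over the grid or autocorrelated.
- Each MAD cohort is one group. The MAD power runs use the SAD sampling grid.

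**Statistic.** H = [12 / (N(N+1))] x sum(R_i^2 / n_i) - 3(N+1), divided by the tie correction 1 - sum(t^3 - t) / (N^3 - N), and referred to chi-square on (groups - 1) df. SAD with placebo: N = 30, 5 df. Active only: N = 20, 4 df. There were 2,500 to 3,000 runs per scenario. Calibration with placebo distributed like active gave 3.6% rejection (SAD) and 4.2% (MAD).

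**Why power falls.** With active centres from 72 to 144 h, active values span 48 to 336 h. Under uniform noise, 4/11 of placebo times lie below that span and 2/11 above it. So 10 x 6/11 = 5.5 of the 10 placebo subjects are expected to take the outermost ranks.

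**Real dose difference**

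| Part | Nadir centres by group (h) | Active only | With placebo |
|---|---|---|---|
| SAD | 72/72/96/144/144 | 98% | 30-34% |
| SAD | 72/96/96/96/144 | 63-64% | 12-16% |
| SAD | 72/72/96/96/96 | 39-42% | 8-14% |
| SAD | 96/96/96/96/144 | 22-23% | 5-10% |
| MAD | 72/96/96/144 | 96% | 58-63% |
| MAD | 72/72/96/96 | 68-69% | 30-37% |
| MAD | 72/72/144/144 | 100% | 96-98% |

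With a different assumed SAD trend, running from 96 h to 336 h, power was 86-87% active only and 31-42% with placebo. With a weak trend the two tests were close (25-27% against 20-27%).

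**No dose difference, SAD, placebo included**

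| Common nadir | Rejection |
|---|---|
| 96 h | about 5% |
| 144 h | 11-14% |
| 336 h | 26-34% |

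Active only, the rate is 2-5%. The upper rows depend on the noise model. Across all models tried, the 144 h rate ranged from 2% to 14%. A repeat with noise strongly correlated over clock time, which favours late placebo minima, brought the 336 h rate back to about 5%. The same repeat left power for the first SAD shift at less than half its active-only value.

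**No dose difference, MAD, within a 7-day interval.** If active nadirs fall at the last one or two samples, the test with placebo rejects in 57-100% of runs under uniform noise and 5-73% under late-weighted noise.

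**The case against.** **The SAD text claims only a treatment-group comparison.** This stands. If placebo differs from active, rejecting that null is correct, and measuring the rejection rate against 5% applies a null that the SAD text does not state. Only the MAD wording turns the result into a statement about dose.

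**A reader might infer that the test often rejects without a dose effect.** The documents do not support that. They give no nadir distribution, and for a 96 h nadir the SAD rate is near nominal. High rates need nadirs away from the middle of the placebo scatter.

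**The pairwise step sorts out the source.** Largely true. With identical active doses in SAD, the gate opened in 5-33% of simulated trials, but the gate opening together with any false dose-to-dose result occurred in 0.3-3.3%, against 0.5-3.8% with an active-only gate. The harm that remains is lost power and a misleading label, not an excess of false dose-to-dose claims.

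**A reader might infer that the choice of MAD doses was compromised**, because footnote 3 to the Part 2 table says those doses "are based on the lowest observed IgG measurement (IgG nadir) and time to IgG nadir". The same footnote describes a review of blinded data. A test with placebo as a separate group needs the allocation, so it was not the input to that choice.

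**Placebo may not be the largest MAD group.** It is largest if each cohort is a group. Cohorts 8 and 10 share a planned regimen, and if combined they would give 12 active subjects. The meaning of placebo tEmax is unaffected.

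**Conclusion.** The concern holds in a limited form. In both parts pooled placebo is a ranked group, the largest when each cohort stands alone, in a test of a quantity that has no drug-related meaning under placebo, and that test gates the pairwise comparisons. The firm result is loss of power for moderate to clear dose differences: it appeared under every placebo noise model tried, for example 98% to about 30-34% in SAD. Very large shifts survive, and weak ones lose less in absolute terms because there is little power to lose. Rejection without any dose difference is possible but conditional on where the nadir falls and how the noise behaves.

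All percentages rest on assumed alpha, nadir and noise distributions, since the protocol gives none. Severity is minor: pharmacodynamics is a secondary objective, tEmax is one of several derived parameters, the trial is not powered for any test, and percent change, AUEC and Emax, where placebo is a proper comparator, are analysed separately.

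**What to change.** In the SAD and MAD paragraphs on tEmax, replace the pooled-placebo phrase so that the Kruskal-Wallis test and the pairwise Wilcoxon tests cover the active dose groups only. Report placebo tEmax descriptively. Keep pooled placebo in the ANOVA for percent change, AUEC and Emax. The MAD reference to a dose effect then describes what is tested.

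The cost is one phrase in each paragraph, with no change to data or visits and no loss of level control (2-5% rejection under no dose difference). One limit remains: an active dose too low to reduce IgG has the same uninformative tEmax. When the lowest SAD dose was simulated as pure noise with the rest at 144 h, rejection was 8-19% active only and 3-16% with placebo, so the change does not solve that case.

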#### Safety

- The following safety parameters will be tabulated and analyzed descriptively: adverse events, clinical laboratory tests, ECGs, physical examinations, and vital signs.
-

### TIME AND EVENTS SCHEDULE: PART 1

Time of Visit (days)	Screening a	Day -1	Day 1		Day 2	Day 3	Day 4	Day 5	Day 7	Day 15	Day 22	Day 29 / Follow-up Visit		
			Hours relative to start of study drug infusion											
Time From Dose			0h b	2h c	4h	8h	24h	48h	72h	96h	144h	336h	504h	672h
Informed consent d	X													
In-/exclusion criteria	X	X												
Medical history/ concomitant diseases	X													
Demographic data	X													
Physical examination	X e	X e	X g				X			X				X
Vital signs f	X	X	X g	X	X	X	X		X	X	X	X	X	X
Single 12-lead ECG	X	X	X g	X	X	X	X		X	X	X	X	X	X
Clinical laboratory tests h	X		X g				X	X	X	X	X	X	X	X
Serum albumin determination			X g	X	X	X	X	X	X	X	X	X	X	X
Lymphocyte typing: B, T subset and NK cells	X		X g	X	X	X	X		X		X	X	X	X
Urinalysis	X		X g				X		X	X	X	X	X	X
Pharmacokinetics: Blood			X g	X	X	X	X	X	X	X	X	X	X	X
Pharmacokinetics: Urine collection i		X	X						X					
Pharmacodynamics j			X g	X	X	X	X	X	X	X	X	X	X	X
Anti-drug antibodies (ADA)			X g							X	X	X	X	X
Urine drug screen and alcohol breath test k	X	X												
Pregnancy test l	X	X												X
Virology/Bacterial screen m	X													
Randomization			X g											
Administration of study drug n			X											
Confinement		Check-in								Check-out o				
Concomitant therapies p	X													X
Adverse events p	X													X

a. To take place between 1 and 28 days prior to

administration of study drug.

b. 0h represents the start of infusion of study drug.

- c. Assessments to take place immediately following end of study drug infusion.
- d. No study-related assessment is to be carried out before signing of the informed consent form.
- e. Includes weight, height and BMI at screening and weight only on Day-1.
- f. Blood pressure and pulse rate (supine) and oral body temperature.
- g. Assessments should be completed pre-dose.
- h. Blood samples for safety assessments should be taken after an overnight fast (fasting for at least 10h) for unbiased glucose determination. Safety assessments to include Biochemistry, and Hematology.
- i. Urine PK collections to be taken between first void (at which the subjects empty their urinary bladder) until 0 hours pre-dose and according to the following windows postdose: 0-4h, 4-8h, 8-12h, 12-24h, 24-48h, 48-72h.
- j. Total IgG, IgG subtypes (IgG 1, IgG 2, IgG 3, and IgG 4), IgA, IgD, IgE and IgM.
- k. Urine drug screen will test for: amphetamines, barbiturates, benzodiazepines, cannabis, cocaine, opiates, methadone, and tricyclic antidepressants.
- l. For women, a serum pregnancy test at screening and urine pregnancy test at other visits will be performed.
- m. Includes HbsAg and anti-HCV antibodies, HIV antibodies and TB serology.
- n. Study drug will be administered as an IV infusion over 2h.
- o. Subjects will be released from the unit once review (clinical laboratory test, albumin, physical examination, vital signs and ECG) has been completed of all Day 5 safety assessments.
- p. Adverse events and intake of concomitant medication(s) will be monitored continuously from informed consent signature until the last study-related activity.

**TIME AND EVENTS SCHEDULE: PART 2: 4-DAY DOSING INTERVAL (COHORT 7)**

Time of Visit (days)	Screening a	Day -1	Days 1, 5, 9, 13 b , and 17								Day 21	Day 22	Day 23	Day 24	Day 25	Day 27	Day 30	Day 35	Day 42	Day 49 / FU Visit	Day 63 / FU Visit s,t	Day 77 / FU Visit s,t
			Hours relative to start of study drug infusion								Hours relative to start of study drug infusion											
			0h c	2h d	4h	8h	12h	24h	48h	72h	0h	24h	48h	72h	96h	144h	216h	336h	504h	672h	1008h	1344h
Informed consent e	X																					
In-/exclusion criteria	X	X																				
Medical history/ concomitant diseases	X																					
Demographic data	X																					
Physical examination	X f	X f	X h							X h	X			X		X			X	X	X	
Vital signs g	X	X	X h	X	X	X	X	X	X	X h,i	X	X	X	X	X		X	X	X u		X	
Single 12-lead ECG	X	X	X h	X	X	X	X	X	X	X h,i	X	X	X	X	X		X	X	X u		X	
Clinical laboratory tests j	X		X h					X		X h	X		X		X	X	X	X	X	X	X	
Serum albumin determination			X h			X		X		X h	X	X	X	X	X	X	X	X	X	X	X	
Lymphocyte typing: B, T subset and NK cells	X		X h					X		X h	X			X		X	X		X	X	X	
Urinalysis	X		X h					X		X h	X		X		X	X	X	X	X	X	X	
Pharmacokinetics: Blood			X h	X		X		X	X	X h,i	X	X	X	X	X	X	X	X	X	X	X	
Pharmacodynamics k			X h	X		X		X	X	X h,i	X	X	X	X	X	X	X	X	X	X	X	
Anti-drug antibodies (ADA)			X h							X h			X		X		X	X	X			
Urine drug screen and alcohol breath test l	X	X																				
Pregnancy test m	X	X																	X u		X	
Virology/Bacterial screen n	X																					
Randomization			X o																			
Administration of study drug p			X								X											

Confinement		Check-in															Check-out g														
Concomitant therapies f	X																												X	X	X
Adverse events r	X																												X	X	X

- a. To take place between 1 and 28 days prior to administration of study drug.
- b. The following assessments will not be completed on Day 13: serum albumin determination, lymphocyte typing, vital signs, and ECG.
- c. 0h represents the start of infusion of study drug.
- d. Assessments to take place immediately following study drug infusion.
- e. No study-related assessment is to be carried out before signing of the informed consent form.
- f. Includes weight, height and BMI at screening and weight only on Day -1.
- g. Blood pressure and pulse rate (supine) and oral body temperature.
- h. Assessments should be completed pre-dose on all study drug infusion days.
- i. On Day 21, assessments should follow the same postdose collection schedule (at 2h, 4h, 8h, and 12h postdose where applicable) as for Days 1, 5, 9, 13 (where applicable), and 17.
- j. Blood samples for safety assessments should be taken after an overnight fast (fasting for at least 10h) for unbiased glucose determination.
- k. Total IgG, IgG subtypes (IgG 1, IgG 2, IgG 3, and IgG 4), IgA, IgD, IgE and IgM.
- l. Urine drug screen will test for: amphetamines, barbiturates, benzodiazepines, cannabis, cocaine, opiates, methadone, and tricyclic antidepressants.
- m. For women, a serum pregnancy test at screening and urine pregnancy test at other visits will be performed.
- n. Includes HbsAg and anti-HCV antibodies, HIV antibodies and TB serology.
- o. Randomization to be completed pre-dose on Day 1 only.
- p. Study drug will be administered as an IV infusion over 2h every 4 days (96h) (i.e., on Days 1, 5, 9, 13, 17 and 21). The dosing interval for the Part 2 MAD Cohort 9 will be chosen following review of the blinded data from the Part 2 MAD Cohort 8 (see Section 3.4.2).
- q. Subjects will be released from the unit once review (clinical laboratory tests, albumin, physical examination, vital signs and ECG) has been completed of all Day 25 safety assessments.
- r. Adverse events and intake of concomitant medication(s) will be monitored continuously from informed consent signature until the last study-related activity.
- s. These visits can be planned with a window of ± 2 days.
- t. Not applicable for Cohort 9.
- u. Only applicable for Cohort 9 and for subjects in Cohort 7 who do not consent to the additional visits added in this amendment.

## **TIME AND EVENTS SCHEDULE: PART 2: 7-DAY DOSING INTERVAL (COHORT 8, COHORT 9, AND COHORT 10)**

Time of Visit (days)	Screening a	Day -1	Days 1, 8, and 15								Day 22	Day 23	Day 24	Day 25	Day 27	Day 28	Day 31	Day 36	Day 43	Day 50 / FU Visit	Day 64 / FU Visit d,e	Day 78 / FU Visit d,e	
			Hours relative to start of study drug infusion								Hours relative to start of study drug infusion												
			0h b	2h c	4h	8h	12h	24h	72h	120h	0h	24h	48h	72h	120h	144h	216h	336h	504h	672h	1008h	1344h	
Informed consent f	X																						
In-/exclusion criteria	X	X																					
Medical history/ concomitant diseases	X																						
Demographic data	X																						
Physical examination	X g	X g	X i							X i	X			X		X			X	X	X		
Vital signs h	X	X	X i	X	X	X	X	X	X	X ij	X	X	X	X	X		X	X	X k		X		
Single 12-lead ECG	X	X	X i	X	X	X	X	X	X	X ij	X	X	X	X	X		X	X	X k		X		
Clinical laboratory tests l	X		X i					X	X	X	X i	X		X		X	X	X	X	X	X	X	
Serum albumin determination			X i					X	X	X	X i	X	X	X	X	X	X	X	X	X	X	X	
Lymphocyte typing: B, T subset and NK cells	X		X i				X		X	X i	X			X		X	X		X	X	X		
Urinalysis	X		X i				X		X	X i	X		X		X	X	X	X	X	X	X	X	
Pharmacokinetics: Blood			X i	X		X		X	X	X	X ij	X	X	X	X	X	X	X	X	X	X	X	
Pharmacodynamics m			X i	X		X		X	X	X	X ij	X	X	X	X	X	X	X	X	X	X	X	
Anti-drug antibodies (ADA)			X i								X i			X		X		X	X	X			
Urine drug screen and alcohol breath test n	X	X																					
Pregnancy test o	X	X																		X k		X	
Virology/Bacterial screen p	X																						
Randomization			X q																				
Administration of study drug r			X								X												

Confinement		Check -in																	Check -out s													
Concomitant therapies t	X																												X	X	X	
Adverse events t	X																												X	X	X	

- a. To take place between 1 and 28 days prior to administration of study drug.
- b. 0h represents the start of infusion of study drug.
- c. Assessments to take place immediately following study drug infusion.
- d. These visits can be planned with a window of ± 2 days
- e. Not applicable for Cohort 9.
- f. No study-related assessment is to be carried out before signing of the informed consent form.
- g. Includes weight, height and BMI at screening and weight only on Day -1.
- h. Blood pressure and pulse rate (supine) and oral body temperature.
- i. Assessments should be completed pre-dose on all study drug infusion days.
- j. On Day 22, assessments should follow the same postdose collection schedule (at 2h, 4h, 8h, and 12h postdose where applicable) as for Days 1, 8, and 15.
- k. Only applicable for Cohort 9.
- l. Blood samples for safety assessments should be taken after an overnight fast (fasting for at least 10h) for unbiased glucose determination.
- m. Total IgG, IgG subtypes (IgG 1, IgG 2, IgG 3, and IgG 4), IgA, IgD, IgE and IgM.
- n. Urine drug screen will test for: amphetamines, barbiturates, benzodiazepines, cannabis, cocaine, opiates, methadone, and tricyclic antidepressants.
- o. For women, a serum pregnancy test at screening and urine pregnancy test at other visits will be performed.
- p. Includes HbsAg and anti-HCV antibodies, HIV antibodies and TB serology.
- q. Randomization to be completed pre-dose on Day 1 only.
- r. Study drug will be administered as an IV infusion over 2h every 7 days (i.e., on Days 1, 8, 15, and 22). The dosing interval for the Part 2 MAD Cohort 9 will be chosen following review of the blinded data from the Part 2 MAD Cohort 8 (see Section 3.4.2).
- s. Subjects will be released from the unit once review (clinical laboratory tests, albumin, physical examination, vital signs and ECG) has been completed of all Day 25 safety assessments.
- t. Adverse events and intake of concomitant medication(s) will be monitored continuously from informed consent signature until the last study-related activity.
